**- V4/Follow-up visit (Week 24/Week 28 +/- 14 days),**

**- V5/Follow-up visit (Week 48/Week 52 +/- 14 days), and**

**- V6/Follow-up visit/End of study visit (Week 72/Week 76 +/- 14 days):** At these visits, the following procedures will be performed:

- Assessment of concomitant medication/cosmetic procedures on the face and non-drug treatments.
- Assessment of AEs/SAEs.
- [REDACTED]
- Assessment of iGAIS and sGAIS.
- Assessment of severity of each investigated region according to the corresponding MAS by the blinded rater.

 - confidential -	Merz Pharmaceuticals GmbH	M900391005/RaLido
	Clinical Protocol for post market clinical follow-up studies (PMCF)	

**Table 7: Overview of study activities/visit schedule**

MRZ 900391005	Base-line	Follow-up/ optional touch-up	TC Follow-up	Prim. endpoint visit	Optional prim. endpoint visit	Follow-up visits	Final study visit e
Visit	V1	V2	V2A b	V3 c,d	V3A c	V4 c,d and 5 c,d	V6 c,d,e Final study visit
Timepoint	Day 1	Week 4	Week 8	Week 12/16	Week 16	Weeks 24/28 and 48/52	Week 72/76
Visit window		± 7 days	± 7 days	± 7 days	± 7 days	± 14 days	± 14 days
Informed consent	X						
Inclusion/exclusion criteria	X						
Exclusion criteria N° 12, 17, 30		X b					
Demographics	X						
Relevant medical history/concomitant diseases	X						
Previous & concomitant medications/treatm.	X	X	X	X	X	X	X
Photographs	X						
Determination of treatment indications	X	X b					
iGAIS/sGAIS		X		X	X	X	X
MAS (blinded rater)	X a	X		X	X	X	X
MAS (treating invest.)	X a						
Injection/touch-up	X	X b					
██████████ ██████████ ██████████ ██████████	■	■					
AEs /SAEs	X	X	X	X	X	X	X
Device deficiencies, technical complaints	X	X					

a MAS of blinded rater needs to be confirmed by the treating investigator prior SMD application;

b in case of optional touch-up;

c for subjects with no touch-up, primary endpoint will be assessed at Week 12. For subjects with touch-up in all indications treated at Day 1, primary endpoint will be assessed at Week 16. For patients with partial touch-up (in at least one indication, but not in all indications treated at Day 1), the primary endpoint for the indications that did not receive touch-up will be

 - confidential -	Merz Pharmaceuticals GmbH M900391005/RaLido	
	Clinical Protocol for post market clinical follow-up studies (PMCF)	Version 1.0 18-Jun-2018

assessed at Week 12 and for the indications that received touch-up will be assessed during the additional visit V3A at Week 16, follow-up visits will occur at Weeks 28, 52, and 76;

- d if all indications treated at V1 are also treated at the optional touch-up, V3, 4, 5, and 6 will be at Weeks 16, 28, 52 and 76, respectively;
- e in case of premature study discontinuation a final study visit has to be performed for the subject.

 - confidential -	Merz Pharmaceuticals GmbH	M900391005/RaLido
	Clinical Protocol for post market clinical follow-up studies (PMCF)	

## 10 SAFETY ASSESSMENTS

### 10.1 Definition of an adverse event (AE)

An AE is any untoward medical occurrence, unintended disease or injury, or untoward clinical signs (including abnormal laboratory findings) in subjects, users or other persons, whether or not related to the investigational medical device.

NOTE 1 This definition includes events related to the investigational medical device or the comparator.

NOTE 2 This definition includes events related to the procedures involved.

NOTE 3 For users or other persons, this definition is restricted to events related to investigational medical devices.

#### 10.1.1 Adverse event details

The period of observation for an AE extends from when the informed consent form was signed until the last study visit of the subject. Any medical occurrence that happens between the time when the informed consent form is signed and the first treatment with the SMD is an AE and has to be documented in the subject's file and in the eCRF AE report form. Any AE observed will be fully investigated, documented and followed up until the event is either resolved or adequately explained. In cases of surgical or diagnostic procedures, the condition/illness leading to such a procedure is considered as the adverse event rather than the procedure itself. New AEs reported to the investigator during the observational period, after the last treatment with the SMD, must be documented, treated, and followed up like all other AEs.

AEs will not be followed up after the final visit, which is scheduled 72 or 76 weeks (depending on optional touch up) after first treatment with the SMD.

Treatment emergent adverse events (TEAEs) are defined as adverse events with onset or worsening at or after the first administration of study treatment.

Pre-existing conditions noted in the medical history and previous to SMD administration should not be reported as an AE, unless the condition worsens or the disease reoccurs during the reporting period. To determine whether a condition has worsened, it is compared to the condition of the subject at screening.

 - confidential -	Merz Pharmaceuticals GmbH	M900391005/RaLido
	Clinical Protocol for post market clinical follow-up studies (PMCF)	Version 1.0 18-Jun-2018

### **10.1.2 Adverse event handling and reporting**

Data pertaining to AEs will be collected during each investigation visit based on the subject's spontaneous description, through investigator inquiry, or discovered in the course of examinations done during the visit. The investigator will assess and record any AE in detail in the subject file and on the eCRF AE report form. The following information must be recorded:

- AE diagnosis or main symptom.
- Location of AE: systemic or restricted to injection area. In case of local reaction, the corresponding area should be reported.
- Date of onset.
- Date of worsening.
- Severity (maximum observed; see Section [10.1.3](#)).
- Causal relationship (not related, related).
- Serious (yes or no).
- Outcome (see Section [10.1.5](#)).
- Action taken with SMD
- AE leading to discontinuation of the investigation (yes or no).
- Stop date.

After completion of all scheduled visit assessments the investigator must document any AEs arising from these assessments.

In case of an serious adverse event (defined in section [10.2](#)), the investigator must also complete an SAE report form and report it to the CRO immediately, as described in Section [10.2.2](#).

### **10.1.3 Adverse event severity grading scale**

The clinical severity of an AE will be classified as:

 - confidential -	Merz Pharmaceuticals GmbH	M900391005/RaLido
	Clinical Protocol for post market clinical follow-up studies (PMCF)	Version 1.0 18-Jun-2018

**Mild:** Signs and symptoms that can be easily tolerated. Symptoms can be ignored and disappear when the subject is distracted.

**Moderate:** Signs and symptoms that cause discomfort and interfere with normal functioning, but are tolerable. They cannot be ignored and do not disappear when the subject is distracted.

**Severe:** Signs and symptoms that affect usual daily activity and incapacitate the subject, thereby interrupting his/her daily activities.

The Investigator is required to grade the severity/intensity of each AE.

#### **10.1.4 Causal relationship with medical device**

An AE is considered to be “related” to SMD if a causal relationship between the SMD and an AE is at least reasonably possible (i.e., the relationship cannot be ruled out). In this case the event is considered an “adverse device effect” (see Section 10.3). If the event is serious (see above), it is a “serious adverse device effect”(see Section 10.4).

The expression “reasonable causal relationship” is meant to convey that there are facts (evidence) or arguments to suggest a causal relationship. Otherwise, the relationship should be considered as “not related.”

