### 4.3 Risk analysis and risk-benefit assessment

#### Benefits

- CaHA is a biodegradable material [Pavicic 2015]; undesirable effects such as overcorrection of the treated area or dissatisfaction with the outcome of the corrective procedure subside spontaneously after a few months.
- AEs seen in clinical trials with CaHA were generally expected, mild in nature, and short in duration [Kadouch 2017, Rayess 2017, Sadick 2007]. Long-term follow-up studies showed the favorable safety profile of CaHA with mostly injection-related mild side-effects [Bass 2010].
- Allergies and immunological reactions due to CaHA occur very rarely compared to permanent filler materials [Kadouch 2017, Rayess 2017, Sadick 2007]. The risk to develop an allergic reaction to lidocaine is also considered low [Fathi 2016].
- The addition of lidocaine to CaHA provides better patient comfort during treatment [Schachter 2016].
- CaHA has some additional benefits over HA fillers such as longer lasting results and enhanced cellular and extracellular matrix proliferation [Yutskovskaya 2014, Zerbinati 2018].
- Treatment with CaHA provides a high long-term patient satisfaction [Fakhre 2009].
- Treatment with injectable devices is performed on an ambulatory basis. No special preparations for the procedure are required.
- Injection with CaHA is less invasive and less permanent than available invasive treatment options via plastic surgery.

The SMD is CE-marked in Europe and approved in US and several LATAM- and APAC countries. Risks:

In occasional cases, one or more of the events described below may occur either immediately or as a delayed reaction:

 - confidential -	Merz Pharmaceuticals GmbH	M900391005/RaLido
	Clinical Protocol for post market clinical follow-up studies (PMCF)	

- For any implant material, possible adverse reactions that may occur include, but are not limited to, the following: inflammation, infection, fistula formation, extrusion, hematoma/ecchymosis, seroma, induration formation, inadequate healing, skin discoloration/blanching of the skin, inadequate or excessive augmentation, contour irregularity, lumps, granulomas, hardening of the tissue at the injection site. Irregularity of the implant may require a surgical procedure to correct. In extreme cases, overcorrection can lead to site rupture. Overcorrection is not allowed in this study.

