	Clinical Protocol for post market clinical follow-up studies (PMCF)	Version 1.0 18-Jun-2018

up can be performed after four weeks at V2 in the indications that were treated at Day 1, to obtain an optimal aesthetic outcome, as appropriate.

If the subject fulfills the inclusion criteria and agrees to participate, he/she will attend six visits (if no touch-up is performed), six visits plus one telephone contact [TC] (if touch-up is performed in all indications that were treated at Day 1), or seven visits plus one TC (if partial [i.e. in at least one, but not in all indications that were treated at Day 1] touch-up treatment is performed) in total. If any serious AE [SAE] related to the injection or the SMD is not resolved by the end of the study, the subject will be followed until the resolution of the SAE by the Merz Pharmaceuticals Department of Product Safety.

An interim analysis report is planned on 6 months data (Week 24/28 respectively, depending on touch-up).

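### Protocol 10.1.4 gives two thresholds for a related adverse event that disagree on uncertain events, so the same event can be an adverse device effect at one site and unrelated at another

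*Protocol*

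**What the plan says.** Protocol Section 10.1.4 governs causality. Its first paragraph makes an AE related to the study medical device (SMD) when a causal link is "at least reasonably possible (i.e., the relationship cannot be ruled out"). Such an event is an ADE, and a SADE if serious. The second paragraph explains the expression *reasonable causal relationship* as meaning that "there are facts (evidence) or arguments to suggest a causal relationship". It then adds: "Otherwise, the relationship should be considered as “not related".

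The surrounding sections are not uniform on what the relationship is to:

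- Section 10.1, Note 2, on the AE definition: "This definition includes events related to the procedures involved".
- Section 10.1.2 lists a single binary item for each AE: "Causal relationship (not related, related"). It also asks for location, and for the area concerned if the reaction is local.
- Section 10.3 ties an ADE to the use of the device. Its notes extend this to inadequate instructions, deployment, implantation and use error.
- Section 6.1, repeated in SAP Section 3.1, provides for follow-up beyond the study when a serious AE "related to the injection or the SMD is not resolved by the end of the study".
- SAP Section 7.2.1 tabulates TEAEs by worst causal relationship to the product, and separately by affected area. A missing relationship is set to related.

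**The concern.** A causality rule is needed mainly for events where the answer is unclear, and there the two paragraphs of Section 10.1.4 have opposite defaults. Under the first, doubt leads to *related*. Under the second, absence of positive evidence leads to *not related*.

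This matters more here than in a controlled trial. There is no comparator, so attribution rests on each investigator's judgement, made at 15-20 sites. The rationale (Section 4.2) includes detecting emerging risks, and the 18 to 19 months of observation were chosen to capture late-onset reactions (Section 6.2). With a late or previously unknown reaction, positive evidence is likely to be thin at first.

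The scope of the relationship is a lesser, connected point. Section 10.1.4 speaks of the SMD, Section 10.3 of its use, and Section 6.1 of the injection or the SMD. Section 4.3 describes long-term experience with this class of filler as a favourable profile "with mostly injection-related mild side-effects", so sites should not have to guess whether an injection effect counts.

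**Working it through.** **The plan's own figures.** The only safety calculation is in Section 12.1: 161 subjects and a true incidence of 1%. The formula is 1 − (1 − p)^n = 1 − 0.99^161 = 0.8017, which matches the stated 80%. The stated power also reproduces: 0.896 × 0.926 × 0.966 = 0.8015, against 80.1%. Neither figure uses the causality item, so neither changes.

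**The two paragraphs of Section 10.1.4 side by side.**

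| Event | First paragraph | Second paragraph |
|---|---|---|
| Link can be ruled out, nothing supports it | not related | not related |
| Link cannot be ruled out, some fact or argument supports it | related | related |
| Link cannot be ruled out, no fact or argument supports it | **related** | **not related** |

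The conflict is confined to the third row. The second paragraph cannot be read simply as a gloss on the first. The expression it defines does not appear in the first paragraph, which already carries its own, different gloss.

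**What depends on the third row.**

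1. ADE or SADE status (10.1.4, 10.3, 10.4).
2. The sponsor's reporting of SADEs as incidents (10.2.2).
3. Whether a serious event after the observational period has to be reported, since this turns on the investigator's view of relatedness (10.2.2).
4. The TEAE table by causal relationship (Protocol 12.4.2.1, SAP 7.2.1). With one binary field, classifications made under the two rules cannot be separated afterwards.

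**What does not depend on it.**

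1. Overall TEAE incidence, the main analysis of the primary safety variable, which ignores causality.
2. The three responder tests.
3. Reporting of serious events during the study, required whatever the causality (10.2.2).
4. Follow-up of serious events under 10.2.2, which continues until resolution or a plausible explanation, with no causality condition.

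**Follow-up statements.** Section 6.1 and SAP 3.1 make post-study follow-up of an unresolved serious event conditional on relatedness. Section 10.2.2 sets no such condition. Section 10.1.1 follows AEs until they are resolved or explained, but also ends AE follow-up at the final visit. These passages do not fit together as written.

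**Size.** The documents give no expected number or share of third-row events, so no count can be derived.

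**The case against.** The strongest reply is that the gap is narrow. The second paragraph accepts arguments as well as facts, and timing, location or plausibility may serve as an argument. Much of what an investigator would hesitate over is then related under both paragraphs. This stands as a limit on size. For instance, a reader might offer a late nodule, paresthesia or headache as a disputed event. Section 4.3 already lists these among events reported with the product without lidocaine, in trials, after approval or both, so an argument is to hand. It does not remove the conflict, because the closing default of the second paragraph still contradicts the first wherever no such argument exists. Section 11.1 promises training and standardisation across sites, but nothing says which rule would be taught.

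Two stronger readings are tempting, and the documents do not support them:

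- **That the injection-or-SMD follow-up trigger is unworkable.** The trigger covers either cause, the minimum serious-event report asks for the link with treatment, and 10.2.2 follows every serious event in any case. What remains is that the passages need reconciling.
- **That injection-procedure events have no place in the data, or could freely be recorded as unrelated.** Section 10.3 reaches use, deployment, implantation and use error. Section 4.3 lists hematoma among possible reactions to any implant, and needles are packed with the syringe (8.1.1). Location is recorded, and SAP 7.2.1 tabulates events by area. Location is not attribution, and an injury after a correctly performed injection is not named in 10.3, so a clarifying sentence is still useful.

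The eCRF and the serious-event form are not among the documents and may already carry a procedure item. The SAP's rule for missing causality is an imputation convention and does not settle which threshold was meant.

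**Conclusion.** The point holds as a conflict in a stated rule, limited to events that cannot be ruled out but have no positive support. For those events Section 10.1.4 permits both answers, and sites may differ without either departing from the text. The effect is on ADE and SADE classification, incident reporting, reporting of serious events after the observational period, and the causal-relationship table. The primary safety incidence and the confirmatory analyses are unaffected. The extent is unknown and may be small if investigators read *arguments* generously. The conclusion rests on the wording of Section 10.1.4 alone and assumes that no training material or form outside these documents fixes a single threshold. It should be corrected, because the correction is cheap and the mixed classification cannot be undone from the recorded data.

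**What to change.** 1. Keep one threshold in Section 10.1.4. The simplest way is to delete the second paragraph, so that the first, with its cannot-be-ruled-out gloss, governs.
2. State in Section 10.1.4 that relatedness to the SMD covers its use, including the injection. This brings it into line with Section 10.3 and with the wording of Section 6.1 and SAP Section 3.1.
3. Reconcile the follow-up statements in Section 6.1 (with SAP 3.1), Section 10.1.1 and Section 10.2.2.

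A separate item for relatedness to the procedure, with matching table rows, is optional. It would show more, but nothing in the documents requires it, and the eCRF would have to be checked first.

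The cost is amendment wording and a note to sites. Under the threshold in step 1, the reported rate of related TEAEs may be somewhat higher. If events have already been assessed under the present text, the report should say whether they were reassessed.

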#### **10.1.5 Categories of outcome**

- Recovered/resolved.
- Recovering/resolving.
- Not recovered/not resolved.
- Recovered/resolved with sequelae.
- Fatal.
- Unknown.

If there is more than one AE, only the AE leading to death will be attributed with a “fatal” outcome.

 - confidential -	Merz Pharmaceuticals GmbH	M900391005/RaLido
	Clinical Protocol for post market clinical follow-up studies (PMCF)	Version 1.0 18-Jun-2018

## 10.2 Definition of a serious adverse event (SAE)

A SAE is an adverse event that:

- a) led to death,
- b) led to serious deterioration in the health of the subject, that either resulted in
  - 1) a life-threatening illness or injury, or
  - 2) a permanent impairment of a body structure or a body function, or
  - 3) in-patient or prolonged hospitalization, or
  - 4) medical or surgical intervention to prevent life-threatening illness or injury or permanent impairment to a body structure or a body function,
- c) led to foetal distress, foetal death or a congenital abnormality or birth defect

NOTE: Planned hospitalization for a pre-existing condition, or a procedure required by the CIP, without serious deterioration in health, is not considered a serious adverse event.

### 10.2.1 *Serious adverse event details*

In case of a fatality, the cause of death is considered as the adverse event, and the death is considered as its outcome. In this case, the primary cause of death (the event leading to death) should be recorded and reported as an SAE. "Death" will be recorded as the outcome of this respective event; death will not be recorded as a separate event. Only if no cause of death can be reported (e.g., sudden death, unexplained death), the death per se might be reported as an SAE. In case of death, an autopsy report should be submitted (if available). The date and cause of death should be recorded.

Planned hospitalization for a pre-existing condition is not considered as an SAE. If a subject experiences an additional AE that prolongs a pre-planned hospitalization, this is considered to be an SAE and should also be reported as an SAE. Hospitalizations for elective treatments planned before screening and which are documented in the subject's source data are usually not regarded as SAEs.

Device deficiencies that might have led to an SAE if

- a) suitable action had not been taken, or

 - confidential -	Merz Pharmaceuticals GmbH M900391005/RaLido	
	Clinical Protocol for post market clinical follow-up studies (PMCF)	Version 1.0 18-Jun-2018

- b) intervention had not been made, or
- c) if circumstances had been less fortunate
- are handled under the SAE reporting system.

### **10.2.2 Reporting and handling of SAEs**

All SAEs that occur during the investigation period, whether considered to be related to a SMD or not, must be reported via SAE report form to the CRO within 24 hours of knowledge of the event. The CRO will report the SAE to the sponsor. Further reporting details will be outlined in a separate document.

Although all information required for completion of an SAE report form may not be available within the specified time period, an initial report should be submitted if the following minimal information is available:

- An identifiable subject (number).
- A suspect product and how the treatment relates to the SAE.
- An identifiable reporting source (investigator/investigation site identification).
- An event or outcome that can be identified as serious.

The report must be delivered to the individual(s) listed below.

The address for SAE reporting is:

  
Merz Pharmaceuticals GmbH  
Global Product Safety Department  
[name]  
[name]  
E-Mail: [[contact]](mailto:[contact]) in cc to [[contact]](mailto:[contact])  
Telephone:   
Fax:   
Mobile: 

 - confidential -	Merz Pharmaceuticals GmbH	M900391005/RaLido
	Clinical Protocol for post market clinical follow-up studies (PMCF)	Version 1.0 18-Jun-2018

The investigator must supply further supporting information within 3 days of knowledge of the SAE, and a detailed SAE description is an integral part of this supporting information. Follow-up reports should be sent without delay as an SAE report form (marked as a “follow-up” report) and accompanied by appropriate supporting documentation (e.g., hospital reports). The SAE has to be followed-up until the SAE is recovered/resolved or a plausible explanation is available. The SAE will be followed-up only in the Global Product Safety database after final SAE reconciliation is completed.

SAEs occurring after the end of the observational period need only be reported if the investigator considers the event to be related to SMD.

As this study is considered as PMCF study based on §23b German “Medizinproduktegesetz”, serious adverse device effects (see Section 10.4) need to be reported as incidents as well as near incidents by the sponsor accordingly based on the timelines defined in the current “Medizinproduktesicherheitsplanverordnung”.

